1.0 Background and Rationale

Oral mucositis is a debilitating sequela of treatment in the cancer patient, one that affects oral intake, hygiene, treatment and quality of life. Oral mucositis has been reported in 97% - 100% of patients with head and neck cancer receiving fractionated radiation therapy, in 80% of patients receiving chemotherapy for stem cell transplantation and 50% of patients receiving chemotherapy for lymphoma or solid tumors (1).

Mucositis is caused by damage to submucosal structures leading to endothelial cell damage resulting in abnormalities in mucosal epithelial growth. It is the product of a series of biological processes initiated by cellular damage (in the form of radiation and chemotherapy in the cancer population) causing the early release of an inflammatory cascade, which subsequently activates apoptosis. Clinically, patients manifest early with erythema and discoloration, leading to ulceration in latter stages with pain symptoms ranging from slight discomfort to allodynia preventing oral intake. In chemotherapy patients, symptoms first begin 3-5 days after initiation of treatment, with ulceration approximately two days later and resolution 2 weeks later. In radiation patients with mucositis, escalation of doses beyond 20Gy typically produce signs of mucositis (erythema) and progressively worsen to ulceration as dose increases beyond 30Gy (2). These ulcerations may last up to 4 weeks after completion of treatment (3).

In the cancer population, significant morbidity is associate with mucositis. Infection rates double in patients with mucositis during chemotherapy for solid tumors or lymphoma (4), and ulceration leading to systemic infection is a risk in these immunocompromised patients. A reduction of next dose chemotherapy is twice as common after cycles where patients had mucositis, as well as a 50% longer duration of hospitalization. The estimated cost for hospitalizations per chemotherapy cycle in patients with oral mucositis is \$6,277, versus \$3,893 without (5).

Mucositis decreases oral intake secondary to pain, hastening the need for supplemental nutrition via TPN or gastronomy tube and thus increases the risk of malnourishment and infection.

In light of the significant debility associated with mucositis, proper treatment is critical in the immunocompromised patient. Various oral preparations containing local anesthetics, anti-inflammatories, antimicrobials, antiseptics and mucosal coating agents have been investigated; however, insufficient evidence prevents most from being recommended and used regularly (6, 7).

Methylene blue (MB) has been described in the pain literature as an intradiscal injectate for discogenic low back pain (8), as a treatment of oral lichen planus (9) and as a diagnostic tool for oral cancer and precancerous lesions (10). A case series evaluated the intradermal injection of methylene blue for pruritis ani, and symptoms improved in 96% of the patients and resolved in 65% (11). It is postulated that by controlling neuroinflammation at the microglial level, methylene blue may be useful in diseases such as amyotrophic lateral sclerosis (12).

Anecdotal experience of the use of MB in patients with acute and chronic pain associated to oral mucositis has shown very positive outcomes regarding symptom control and decreasing the need for opiates in patients undergoing cancer therapy seen by our consulting service for intractable pain related to oral mucositis. The primary complaint of all patients has been oral pain compromising different structures including tongue and inner lips, sublingual and oral mucosa. The majority had expressed difficulty with feeding secondary to pain. They also had reported weight loss as a result of decreased oral intake. Multiple patients had been hospitalized for pain and failure to thrive, others had been seen as a requested consultations in the Emergency Department, and others had been outpatient clinic visits. They all had expressed suboptimal pain control despite systemic therapy with opiates. Patients had been instructed to take a mouth full of 0.025%, 0.05% or 0.1% MB diluted in normal saline. The mixture is to be kept in the painful site for five minutes then to gargle and spit. The same steps had been to be reeated every 6 hours. The majority of patients had experienced a sustained decrease of more than 50% in their pain scores at 3 weeks follow up. The morphine equivalent daily dose on those that apply significantly reduced or eliminated. The overall patient satisfaction has been very high and the treatment has been well-tolerated, with sustained analgesia. No alteration of taste or motor function reported; no sensory changes or anesthesia of the healthy mucosa has been found. About 80 patients have been treated with MB with concentrations of 0.025%, 0.05% or 0.1%, and we haven't observed any adverse event at any of concentrations.

We propose a randomized controlled trial comparing 4 intervention arms, including 3 concentrations of Methylene Blue (MB) oral rinse combined with conventional therapy and conventional therapy which includes mouth rinses with local anesthetics and cleaning solutions and systemic analgesics given orally or intravenously. In patients with intractable pain associated with oral mucositis defined as the presence of pain or oral dysfunction despite conventional therapy. To the best of our knowledge, no study of this kind has been performed.

2.0 Study Objective

The primary objective is to evaluate the efficacy of MB in reducing the severity of mucositis-related pain, measured by Numeric Rating Scale (NRS), in cancer patients who underwent or are undergoing chemotherapy or radiation therapy. Patients will be randomized to one of 4 intervention arms, including conventional therapy and conventional therapy plus MB with one of 3 concentrations (0.025%, 0.05% or 0.1%) oral rinse to swish and spit.

2.1 Primary Outcomes:

Oral mucositis pain reduction (measured by using the Numeric Rating Scale (NRS); from 0, representing no pain, to 10, representing the worst possible pain) from baseline to 7 days post treatment. The pain scale is included in the Modified Harris mucositis-related pain assessment tool.

2.2 Secondary Outcomes:

1. Oral functioning (eat, swallow, talk: unable=2, difficulty=1, able=0. Oral functioning score is the total score of 3 categories, ranged 0-6). Scale is included in the Modified Harris mucositis-related pain assessment tool. Measurements are obtained at day 0, 1, 2, and 7.
2. Presence of absence of pain and pain score measured by NRS at day 0, 1, 2, and 7.
3. Number of MB doses needed to achieve pain relief at 0, 1, and 2 days post MB administration
4. Morphine equivalent daily dose (MEDD) used for oral mucositis pain at 2, and 7 days post MB administration.
5. Incidence of untoward side effects immediately after MB administration and at 1, 2, 7 days post MB administration.

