6.5 Data collection

Patients enrolled in the study will be asked to complete a baseline assessment questionnaire in person, including the Modified Harris mucositis-related pain assessment tool. The patient will have subsequent follow-up interviews at 1, 2, 7 days with repeat assessment of the Modified Harris mucositis-related pain assessment tool. Furthermore, on Baseline, Day 0, Day 1, Day 2, Day 7 and Day 30, adverse event will be assessed, and this maybe by telephone or face-to-face in the clinic. The patient's medication use will also be assessed at follow-up, including morphine equivalent daily dose (MEDD) and other reported analgesics used for the treatment of their mucositis-related pain. Lastly, the research team will investigate if any patient reported any side effects from the treatment.

All completed data will be stored electronically in the MD Anderson REDCap system, in a locked file, on password-protected computers. Only research team members will access the files. Subject registration will be entered into CORe database.

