7.3 Secondary Outcomes Analysis

The mean change, from baseline to 7 days, in the Modified Harris mucositis-related pain assessment tool scores and the mean change in oral functioning scores will be compared between study arms, utilizing ANOVA or Kruskal-Wallis test (eat, swallow, talk: unable=2, difficulty=1, able=0. Oral functioning score is the total score of 3 categories, ranged 0-6). We will also determine if there are any differences between arms in presence or absence of pain, pain scores, overall analgesic use (including opiate use primarily used for oral mucositis pain via MEDD measurement), and the incidence of untoward side effects utilizing ANOVA, Kruskal-Wallist, Chi-square test, or Fisher's exact test as appropriate. In addition, to obtain a measure of compliance with MB treatment, we will compare the dropout rate within the MB group to the dropout rate in the conventional therapy group utilizing Chi-square test or Fisher's exact test.

The Investigator is responsible for completing an efficacy/safety summary report and submitting it to the IND office Medical Monitor for review. This should be submitted after the first 5 evaluable patients per arm, complete 7 days of study treatment, and every 5 evaluable patients per arm, thereafter.

In addition, the Patient Drug Administration log will be used to keep the record of drug usage. Duration of pain relief corresponding to each drug use will be collected during the interview, in person for Day 0 and via telephone for Day 1, Day 2, and Day 7. The number of MB doses needed (during the last 24 hours or since the last follow-up) in order to achieve pain relief will be collected on Day 1, Day 2, and Day 7.

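### No baseline MEDD is specified, so the opioid outcome cannot describe within-patient change or baseline balance, and its between-arm comparison gives up precision

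*Combined protocol and SAP*

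**What the plan says.** - **Outcome definition (2.2, item 4):** "Morphine equivalent daily dose (MEDD) used for oral mucositis pain at 2, and 7 days post MB administration". No Day 0 or baseline value is listed.
- **Other outcomes in the same list:** for pain, "Presence of absence of pain and pain score measured by NRS at day 0, 1, 2, and 7"; for oral functioning, "Measurements are obtained at day 0, 1, 2, and 7".
- **Data collection (6.5):** "Patients enrolled in the study will be asked to complete a baseline assessment questionnaire in person, including the Modified Harris mucositis-related pain assessment tool". MEDD appears later in that section: "The patient's medication use will also be assessed at follow-up, including morphine equivalent daily dose (MEDD").
- **Analysis (7.3):** the pain tool and oral functioning scores are compared as mean change from baseline to Day 7. For opioids, the variable is "overall analgesic use (including opiate use primarily used for oral mucositis pain via MEDD measurement"), compared between arms by ANOVA, Kruskal-Wallis, chi-square or Fisher's exact test as appropriate. No change score and no baseline covariate is named.
- **Randomisation (6.3):** the strata are baseline pain and oral functioning score. Opioid use is not a stratum.
- **Rationale (1.0):** earlier clinical experience is summarised as "The morphine equivalent daily dose on those that apply significantly reduced or eliminated".

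**The concern.** The background describes opioid use going down, which is a within-patient change. The planned opioid data begin two days after treatment starts, so they give a level with nothing to compare it against.

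Three things are lost:

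1. **Description of change.** Systemic analgesics are part of conventional therapy in every arm (5.5). A reader will want to know whether a fall in NRS came with rising or falling opioid use. Without a starting dose, this cannot be described within patients.
2. **A check on balance.** Patients come from the Emergency Center, the Pain Management Center and the oncology wards (6.1), so opioid dose at entry may vary widely. With 15 per arm and no stratification on opioid use, sizeable chance differences at entry are plausible and would go unseen.
3. **Precision.** If MEDD at entry predicts MEDD at follow-up, adjusting for it removes variance that the unadjusted tests leave in.

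**Working it through.** **Plan's own figure.** The documents give no power or precision figure for MEDD. The only calculation is for the primary NRS outcome (5.1, 7.1): 15 per arm, means 0, 2, 2.5 and 3, within-group SD 2.5, alpha 0.05.
- Grand mean = 7.5/4 = 1.875. Sum of squared deviations = 3.516 + 0.016 + 0.391 + 1.266 = 5.19.
- SD of the means = sqrt(5.19/4) = 1.14, as stated.
- Noncentrality = 15 × 5.19/6.25 = 12.45. With 3 and 56 degrees of freedom, power is 82.7%, against the stated 83%.

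The figure reproduces. It says nothing about MEDD.

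**Inputs for MEDD.** n = 15 per arm (5.1, 6.3). The correlation rho between baseline and follow-up MEDD is not in the documents; it is assumed and shown from 0.3 to 0.8.

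**Formulas**, relative to a follow-up-only comparison:
- Baseline-adjusted (ANCOVA) variance factor = 1 − rho².
- SE reduction = 1 − sqrt(1 − rho²).
- Equivalent patients per arm = 15/(1 − rho²).
- Raw change-score variance factor = 2(1 − rho).

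| Assumed rho | ANCOVA variance factor | SE reduction | Equivalent n per arm | Change-score variance factor |
|---|---|---|---|---|
| 0.3 | 0.91 | 5% | 16.5 | 1.40 |
| 0.5 | 0.75 | 13% | 20 | 1.00 |
| 0.7 | 0.51 | 29% | 29 | 0.60 |
| 0.8 | 0.36 | 40% | 42 | 0.40 |

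**Illustrative power.** For a pairwise difference of 0.8 SD (an assumed size), two-sided 0.05, 15 per arm and no multiplicity correction, power is 56% with follow-up only. With ANCOVA it is 60%, 68%, 84% and 94% at rho 0.3, 0.5, 0.7 and 0.8. A raw change score gives 43%, 56%, 78% and 92%, so it is worse than follow-up only when rho is below 0.5. The gain comes from adjusting for baseline, not from subtracting it.

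**Balance at entry.** The chance difference in mean baseline MEDD between two arms has SE sqrt(2/15) = 0.37 SD. Under a normal approximation it exceeds 0.5 SD in about 17% of pairwise comparisons. This variation is already part of the unadjusted standard error and should not be counted again as a separate error. What is lost is the ability to see it and adjust for it.

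**The case against.** **The documents are silent; they do not exclude a baseline value.** Section 2.2 lists outcome times and is not a full collection schedule. Section 6.5 says what the baseline questionnaire includes, not everything it contains. Eligibility requires symptoms despite conventional therapy (5.2), so analgesic use must be looked at before entry, and 7.2 summarises treatment variables by arm. This stands as far as wording goes: the gap is that a baseline MEDD is not specified, and a reader should not infer that none will be recorded. It does not close the gap. No section names a baseline MEDD, and the list that omits Day 0 for MEDD gives it for pain and oral functioning. The covariate rule in 7.2 concerns the primary outcome and is triggered only by covariates that differ significantly between arms, which an unrecorded variable cannot do.

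**Randomisation protects the comparison.** This stands. A reader might infer that chance imbalance at entry makes the MEDD comparison biased or invalid. It does not: imbalance of this kind is sampling error that the standard error already includes.

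**The gain may be small.** This also stands. Mucositis changes over days, and the treatment itself may alter MEDD, so a low correlation is possible. At rho 0.3 the SE falls by only about 5%.

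**MEDD is a minor outcome.** It is fourth of five secondary outcomes. The study objective and the power calculation concern NRS alone, and the opioid statement in 1.0 is anecdotal background. The documents do not support treating opioid sparing as a principal claim of the trial.

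**Charts could supply the value later.** No section plans this. The outcome is restricted to opioid used for mucositis pain. That attribution is no easier at baseline than at Days 2 and 7, but it is better asked at the time than reconstructed.

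**Conclusion.** The point holds as a cheap improvement to a secondary outcome. As specified, MEDD has no baseline value and no baseline-adjusted analysis, so the trial can compare opioid use between arms without bias from this source, but cannot describe within-patient change or check balance at entry.

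The precision given up is an SE larger than it need be. Adjustment would reduce it by about 5% to 40% over an assumed correlation of 0.3 to 0.8. The documents do not fix where in that range the trial lies, so the upper figures should not be read as the expected gain. The formulas assume a linear, normal-theory model on the analysed scale. Skew and many zeros make them a guide only.

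The statement about bias concerns the missing baseline alone. The optional control-arm crossover after the Day 2 measurements (6.3) separately affects any Day 7 comparison.

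**What to change.** 1. Add one item to the existing in-person baseline questionnaire: MEDD used for oral mucositis pain in the 24 hours before randomisation. List baseline alongside Days 2 and 7 in 2.2 and 6.5.
2. In 7.3, replace the unadjusted MEDD test with a baseline-adjusted comparison of the four arms: rank-based ANCOVA, or ANCOVA on log(MEDD + 1). Choose one in advance. A plain log is undefined when MEDD is zero, an outcome the background leads one to expect. Do not rely on a raw change score for the test; report change descriptively.
3. Make Day 2 the main comparison, because it precedes the optional control-arm crossover, and Day 7 supportive.
4. Tabulate baseline MEDD by arm.

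**Cost:** one form item, one analysis line and one model degree of freedom (residual 56 to 55 with all 60 patients). Attribution to mucositis pain will rest on patient report, as it already does at Days 2 and 7. Treatment, visits and sample size do not change.

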3.2 Adverse Effects, Precautions, and Contraindications

If used systemically, MB administered intravenously (IV) or orally (PO) in large doses may cause nausea, vomiting, abdominal pain, dizziness, headache, profuse sweating, dyspnea, mental confusion, and irritation at the infusion site (only seen with IV). The most common side effects of oral administration are adverse gastrointestinal effects and dysuria. MB causes a blue-green discoloration to saliva, urine, feces, and skin. The skin stains may be removed by application of hypochlorite solution. MB is contraindicated in patients with known hypersensitivity to MB, women who are or may become pregnant (MB is a teratogen), patients with known or suspected glucose-6-phosphate dehydrogenase (G6PD) deficiency, and those who are taking serotonergic drugs. It should be used cautiously in patients with severe renal impairment. Subcutaneous, intrathecal, and intraspinal route of administration should be avoided. Long-term use of MB is also associated with anemia. Therefore, monitoring of complete blood counts is advised (15). These adverse events have been studied in both large IV and PO administration and appear to be much more limited with oral administration (as above). In our study, the use of 100 mL equals 4 - 6 mouth full doses. It might expose patients to a dose of 2-6 mg of MB if swallowed, trans-mucosal absorption if any, when used in an oral rinse, is considered negligible. Formal toxicity monitoring may not be required. Therefore, formal toxicity monitoring will not be necessary. Safety data will be monitored by principle investigator.

If not available, a pregnancy test will be done in females in child-bearing condition (non-menopausal). This study requires women of child bearing potential to use contraception or abstinence from sex during the treatment period and for 30 days after their last dose. Urine pregnancy test will be obtained within 48 hours of staring the study.

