8.0 Adverse Events Reporting

8.1 Adverse Events (AEs)

All patients will be monitored through weekly in person or by phone calls by the research staff allowing for close monitoring of potential adverse events during treatment. In addition, patients will be given a contact phone number for treatment-related questions.

Research staff will collect toxicity, symptoms, and adherence to study medication schedule weekly. Treatment-related toxicities (NCI Common Terminology Criteria for Adverse Events, version 4) will be monitored by the research staff.

Grade 1 and Grade 2 AEs will not be reported. AEs that are Grade 3 and above that meet the definition for serious adverse events (SAEs) in Section 8.2 will be considered to be serious adverse events (SAEs) and will be reported. SAEs that are unexpected and related (definitely, probably, or possibly related) to MB use will be reported promptly according to institutional policies (see below). SAEs that are either expected or unexpected but unrelated (unrelated or unlikely to be related) to MB use will be summarized on the continuing review report. The principal investigator and the treating physician will determine whether or not an AE is related to the study medication.

If in the course of assessing symptoms, the patient reports severe symptoms, the data collector will determine if the patient's healthcare provider is aware that the patient is experiencing this severe symptom. If the healthcare provider is not aware, the data collector will determine if the patient intends to inform the healthcare provider of the symptom and its severity within 24 hours. If the patient does not intend to inform the health care provider, the data collector will inform the patient that the data collector will let the health care provider know of the severity of the symptom within 24 hours. If in the course of assessing symptoms, the data collector becomes aware of any imminently life-threatening condition that the patient is experiencing, the data collector will let the patient know that data collector will be informing a healthcare provider immediately of the condition. The data collector will then initiate contact with a healthcare provider immediately.

A list of adverse events known to be associated with primary treatment is listed in section 3.2 of the protocol.

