8.22 Reporting SAEs

1. Important medical events as defined above, may also be considered serious adverse events. Any important medical event can and should be reported as an SAE if deemed appropriate by the Principal Investigator or the IND Sponsor, IND Office.
2. All events occurring during the conduct of a protocol and meeting the definition of a SAE must be reported to the IRB in accordance with the timeframes and procedures outlined in “The University of Texas M. D. Anderson Cancer Center Institutional Review Board Policy for Investigators on Reporting Unanticipated Adverse Events for Drugs and Devices”. Unless stated otherwise in the protocol, all SAEs, expected or unexpected, must be reported to the IND Office, regardless of attribution (within 5 working days of knowledge of the event).
3. **All life-threatening or fatal events**, that are unexpected, and related to the study drug, must have a written report submitted **within 24 hours** (next working day) of knowledge of the event to the Safety Project Manager in the IND Office.
4. **Unless otherwise noted, the electronic SAE application (eSAE) will be utilized for safety reporting to the IND Office and MDACC IRB.**
5. **Serious adverse events will be captured from the time of the first protocol-specific intervention, until 30 days after the last dose of drug, unless the participant withdraws consent. Serious adverse events must be followed until clinical recovery is complete and laboratory tests have returned to baseline, progression of the event has stabilized, or there has been acceptable resolution of the event.**
6. **Additionally, any serious adverse events that occur after the 30 day time period that are related to the study treatment must be reported to the IND Office. This may include the development of a secondary malignancy.**
7. **Serious adverse events will be forwarded to FDA by the IND Sponsor (Safety Project Manager IND Office) according to 21 CFR 312.32.**
8. **It is the responsibility of the PI and the research team to ensure serious adverse events are reported according to the Code of Federal Regulations, Good Clinical Practices, the protocol guidelines, the sponsor’s guidelines, and Institutional Review Board policy.**

The MD Anderson “Internal SAE Report Form for Prompt Reporting” will be used for reporting to the MD Anderson IRB.

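### The side-effect outcome is timed from MB administration but tested between arms, so it is undefined for conventional-therapy patients and open to attribution bias against MB

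*Combined protocol and SAP*

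**What the plan says.** Section 2.2 gives the only definition of the side-effect outcome: "Incidence of untoward side effects immediately after MB administration and at 1, 2, 7 days post MB administration". Outcomes 1 and 2 in the same list are timed by study day instead. Section 7.3 then plans to compare between arms "the incidence of untoward side effects utilizing ANOVA, Kruskal-Wallist, Chi-square test, or Fisher's exact test as appropriate". The arms are conventional therapy and three MB concentrations, 15 patients each (6.3).

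On collection, section 6.5 states "Furthermore, on Baseline, Day 0, Day 1, Day 2, Day 7 and Day 30, adverse event will be assessed", with no restriction by arm. It adds that "the research team will investigate if any patient reported any side effects from the treatment". Section 6.3 has staff check for adverse events at every follow-up. Section 8.1 monitors all patients weekly with CTCAE version 4, and has the principal investigator and treating physician judge whether an event is related to the study medication.

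Section 8.1 also notes that "A list of adverse events known to be associated with primary treatment is listed in section 3.2 of the protocol". That section includes the statement "MB causes a blue-green discoloration to saliva, urine, feces, and skin". No section says whether discoloration counts towards outcome 5.

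For serious events, section 8.22 states "Serious adverse events will be captured from the time of the first protocol-specific intervention, until 30 days after the last dose of drug".

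There is no placebo, and section 5.0 blinds only the MB concentration. Controls may cross over to MB after the Day 2 measurements (6.3). Section 7.2 counts those who do in their assigned MB arm for the primary outcome. No such rule is given for side effects.

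**The concern.** A between-arm test needs an outcome that every arm can have on the same terms. Outcome 5 counts events after MB administration, and a control off MB has none. The analyst must therefore decide which of the collected events enter the section 7.3 test, and the only written definition points to MB.

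That choice matters because these patients are receiving chemotherapy or radiation and will have symptoms of their own. If the count is limited to events attributed to MB, a background symptom can count in an MB patient and the same symptom cannot count in a control. Assessors can tell MB from no MB, so nothing in the design evens out the attribution. Discoloration, if counted, can occur only in patients who took MB. The trial's stated comparison is MB plus conventional care against conventional care alone (7.0), and its safety half could then reflect how events were labelled and not what MB does.

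**Working it through.** **The plan's own figure.** The documents give no rate, size or power for side effects. The one computed design figure is 83% power for the primary ANOVA. With means 0, 2, 2.5 and 3, the SD of the means is 1.139 (stated as 1.14). The noncentrality is 60 × (1.139/2.5)² = 12.45, and on 3 and 56 degrees of freedom at 0.05 the power is 82.7%. It reproduces, but it does not bear on side effects.

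**Inputs.** There are 15 controls and 3 × 15 = 45 MB patients (6.3). I use a two-sided Fisher exact test at 0.05, which is one of the tests in 7.3. The proportion r of MB patients with an event attributed to MB is an assumption, varied from 10% to 40%. MB is taken to be truly harmless. The limiting case under attribution-only counting is control at 0/15. Pooling the MB arms is for illustration, since 7.3 says only that arms are compared.

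**Step 1: smallest significant count with control at 0/15.**
- Pooled MB: 11/45 gives p = 0.051 and 12/45 gives p = 0.027. The threshold is 12/45 (27%).
- One MB arm: 4/15 gives p = 0.10 and 5/15 gives p = 0.042. The threshold is 5/15 (33%).

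**Step 2: chance of crossing the threshold.** For the pooled test this is P(X ≥ 12), X ~ Binomial(45, r). For one arm it is P(X ≥ 5), X ~ Binomial(15, r). The four-arm chi-square was simulated (20,000 runs). The last column is the pooled Fisher test when all-cause events are counted in every arm at the same true rate r.

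| Assumed r | Pooled Fisher, control 0 | One MB arm, control 0 | Four-arm chi-square, control 0 | Pooled Fisher, equal capture |
|---|---|---|---|---|
| 10% | 0.1% | 1.3% | 9% | 2.1% |
| 20% | 17% | 16% | 23% | 2.7% |
| 30% | 74% | 48% | 52% | 3.5% |
| 40% | 98% | 78% | 86% | 3.3% |

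**Step 3: is a strict zero needed?** No. With 40% recorded in MB patients and 5% in controls, the pooled Fisher test rejects in 81% of trials. With 40% against 10% it rejects in 59%. These are again assumed rates.

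**Step 4: discoloration.** If it counted and every MB patient showed it, 45/45 against 0/15 gives p = 1.9 × 10⁻¹⁴. This is conditional on a counting rule that the documents do not state.

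**Step 5: the SAE window.** It opens at the first protocol-specific intervention, which can apply in any arm. It closes 30 days after the last dose of drug. A control who never takes MB has no such date, so only the end of the window is undefined.

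**The case against.** The strongest reply is that the timing phrase is loose shorthand for study day. Outcome 4, opioid use in morphine equivalents, is timed from MB administration too, and nobody would conclude that controls have no opioid use. Sections 6.3, 6.5 and 8.1 collect adverse events in all patients, and section 8.22 sends all SAEs to the IND Office whatever their attribution. Conventional therapy is itself one of the four intervention arms and includes rinses and analgesics that can cause side effects, so treatment in section 6.5 need not mean MB.

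Much of this stands. A reader might infer that the conventional arm can have no safety events at all. The documents do not support that, because the events are collected. What the reply does not settle is which collected events the test uses. Opioid use can be measured in a control without any judgement of cause. A side effect cannot be counted until someone says which events qualify, and the one written definition refers to MB.

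A second reply is that the assumed rates are too high. The protocol reports no adverse events in about 80 patients treated with MB (1.0 and 3.1). Taken as 0/80, the two-sided 95% upper limit is 1 − 0.025^(1/80) = 4.5%, and at 5% the pooled test in Step 2 is significant in fewer than 0.1% of trials. That is a fair caution, and the larger figures are scenarios only. The experience is described as anecdotal, though, and is not a rate from scheduled questioning of every patient with CTCAE grading.

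On discoloration, section 8.1 cites section 3.2 as a list of known events and does not make it the definition of outcome 5. A report of no adverse events with a dye suggests that these investigators do not count staining. The plan should say so.

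**Conclusion.** The point holds as a conflict between the definition in section 2.2 and the test in section 7.3. Applied as written, outcome 5 has no meaning for a control off MB. With no placebo, a count of treatment-attributed events would lean against MB.

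The size is conditional. With control at 0/15 and MB harmless, the pooled false-positive rate runs from about 0.1% at an assumed attributed rate of 10% to 98% at 40%. Equal all-cause capture at 30% keeps it at about 3.5%. The documents give no rate with which to choose within that range, and the pooled contrast is not one that section 7.3 specifies for side effects.

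A reader might go further and infer that the test will show harm whatever MB does. The thresholds rule that out, because even a control arm fixed at zero leaves the pooled test non-significant below 12/45. The near-certain result from staining depends on a counting rule that appears nowhere. The missing end of the SAE window is a minor clarification. The main change should be made before analysis, because it removes an avoidable bias at little cost.

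**What to change.** - **Outcome 5 (2.2) and its test (7.3):** define the outcome as the number of randomised patients with any adverse event new or worse than baseline, regardless of attribution, CTCAE-graded, by study day, in all four randomised arms.
- **Timing of the test:** make the between-arm comparison through Day 2, the last assessment before optional crossover. Report Day 7 descriptively by actual MB exposure.
- **Discoloration:** tabulate blue-green discoloration separately and keep it out of the test.
- **Attributed events:** report MB-attributed events descriptively.
- **SAE window:** as a minor clarification, reconcile 8.22 with 6.5 so that the window has a stated end for patients who never receive MB.

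The cost is wording in 2.2, 7.3 and 8.22. Section 6.5 already schedules adverse-event assessment at baseline and Days 0, 1, 2, 7 and 30, so no visits are added. Section 8.1 says that Grade 1 and 2 events will not be reported. One sentence should confirm that they are still recorded, since the new outcome needs them. The real downside is that the Day 7 between-arm side-effect comparison becomes descriptive.
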